10.3 Safety Laboratory Variables

Baseline for all laboratory analyses will be the values obtained at the last assessment prior to the first dose of the investigational medicinal product (IMP). Treatment-emergent laboratory data will include tests completed after the first dose of IMP through the residual time of drug effect. End of trial will include the last post-baseline observation during the trial.

Laboratory variables will be grouped under "Haematology", "Clinical Chemistry" or "Urinalysis"

10.3.1 Summary Statistics

Mean change and mean percentage (%) change from baseline at end of trial will be presented for each laboratory variable. In addition, descriptive statistics, i.e., the number of subjects with data, mean (standard deviation), median, minimum, and maximum values, will be presented for observed values and change from baseline at each time-point for each laboratory variable.

All laboratory parameters, values, units, normal ranges, flags collected (normal/abnormal) in the clinical database will be included in by-patient listings for further medical review.

10.3.2 Laboratory Variable Changes Relative to Normal Range

Changes relative to normal ranges are presented with shift tables with total number of subjects, and number and % of subjects who experienced a shift by treatment period. The following categories for shift tables are defined:

• Low: Values which are below the lower reference range limit;

• Normal: Values which are within the lower and upper reference range;

High: Values which are above the upper reference range limit.
Absent: No value for measured variable (for urinalysis only)

• Present: Any value obtained for measured variable (for urinalysis only)

For all haematology and clinical chemistry variables, shift tables will be prepared to compare baseline values to the worst in-treatment value. More specifically, for haematology and clinical chemistry, tables presenting the changes from *Low* or *Normal* to *High* and from *High* or *Normal* to

Low will be provided. For urinalysis variables, shift tables will summarise the number (%) of subjects who had "absent" values at baseline and "present" values during the treatment period.

10.3.3 Markedly Abnormal Changes

A summary table will be prepared that displays for each laboratory variable the number and percentage of subjects in each treatment group with normal baseline values who had at least one pre-specified markedly abnormal value anytime during the treatment period. Pre-specified markedly abnormal criteria for laboratory tests are given in Section 15.5.

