10.3.5 Urinalysis

Incidence of changes in urinalysis will be summarised by treatment group. A summary table with number of subjects with change from *Absent* at baseline to *Present* during trial will be summarised.

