10.4.1.2 Markedly Abnormal Changes

Summary tables will be prepared displaying the number and percentage of subjects with normal baselines who had one or more pre-specified markedly abnormal treatment-emergent values, according to the definition in Section 15.5.

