15.5 Markedly Abnormal Laboratory Safety Values and Vital Signs

When applying the markedly abnormal criteria defined below, the low/high thresholds will be compared to the laboratory normal reference low/high limits. If the normal reference low limit is smaller than the low threshold, then the normal reference low limit would be used; On the other hand, if the normal reference high limit is larger than the high threshold, then the normal reference high limit would be used.

Table 6: Markedly abnormal Criteria for Laboratory Tests

		Markedly abnormal Criteria		
Variable	Units	Low	High	
Haematology			•	
Haemoglobin	g/L	≤ 115	Not applicable	
Haematocrit	Ratio	≤ 0.37	≥ 0.56	
Total WBC	10 ⁹ /L	≤ 2.8	≥ 16.0	
Eosinophils	%	Not applicable	≥ 10	
Neutrophils	%	≤ 15	≥ 90	
Lymphocytes	%	≤ 10	≥ 80	
Monocytes	%	Not applicable	≥ 20	
Basophils	%	Not applicable	≥ 5	
Bands	%	Not applicable	≥ 20	
Platelets	10 ⁹ /L	≤ 75	≥ 700	
TotalRBC	$10^{12}/L$	≤ 3.5	Not applicable	
Clinical Chemistr	y	•	 	
AST	IU/L	Not applicable	> 3xULN	
ALT	IU/L	Not applicable	> 3xULN	
Alkaline	IU/L	Not applicable	> 3xULN and 25% increase from	
phosphatase			baseline	
GGT	IU/L	Not applicable	> 3xULN	
LDH	IU/L	Not applicable	> 3xULN	
Total bilirubin	μmol/L	Not applicable	≥ 1.5xULN	
Urea nitrogen	mmol/L	Not applicable	≥ 10.7	
Creatinine	μmol/L	Not applicable	≥ 177	
Total protein	g/L	≤ 45	≥ 90	
Albumin	g/L	≤ 25	≥ 65	
Sodium	mmol/L	≤ 130	≥ 155	
Potassium	mmol/L	≤ 3.0	≥ 5.8	
Chloride	mmol/L	≤ 90	≥ 115	
Phosphorus	mmol/L	≤ 0.5	≥ 1.9	
Calcium	mmol/L	≤1.8	≥ 3.9	
Uric acid	mmol/L	Not applicable	≥ 0.62	
Glucose	mmol/L	≤ 2.8	≥ 10	
Totalcholesterol	mmol/L	Not applicable	≥ 8.0	
Urinalysis: Quantitative				

рН	None	≤ 4	Not applicable			
Specific gravity	None	≤ 1.005	Not applicable			
Urinalysis: Dipstick Chemistries						
Glucose	0 - 4+	Not applicable	Increase of 2 or more units from baseline			
Casts		Not applicable	Increase of 2 or more units from baseline			
Protein	0 - 4+	Not applicable	Increase of 2 or more units from baseline			
Ketones	0 - 4+	Not applicable	Increase of 2 or more units from baseline			
Blood (Hgb)	0 - 4+	Not applicable	Increase of 2 or more units from baseline			
Urinalysis: Microscopic Variables						
RBC	no./hpf	Not applicable	≥ 10			
WBC	no./hpf	Not applicable	≥ 20			
Casts	no./hpf	Not applicable	Neg at baseline to positive on-treatment			
Bacteria	no./hpf	Not applicable	Neg at baseline to positive on-treatment			

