Cells	no./hpf	Not applicable	Neg at baseline to positive on-treatment			
Crystals	no./hpf	Not applicable	Neg at baseline to positive on-treatment			

Table 7: Markedly abnormal Criteria for Vital Signs*

Variable	Criterion Value	Change from Baseline
Systolic blood pressure	≥ 180 mmHg	Increase of≥20 mmHg
	≤90 mmHg	Decrease of≥20 mmHg
Diastolic blood pressure	≥ 105 mmHg	Increase of≥15 mmHg
	≤ 50 mmHg	Decrease of≥15 mmHg
Pulse rate	≥ 120 bpm	Increase of≥15 bpm
	≤ 50 bpm	Decrease of≥15 bpm
Body weight	None	Increase of ≥ 7%
		Decrease of≥7%
Body temperature	≥38.3° C	Increase to ≥39.4°C

^{*} To be identified as markedly abnormal, a treatment value must meet the criterion value and also the specified change frombaseline.

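### The markedly-abnormal and laboratory shift counts both leave out a subject who worsens in the same direction from an abnormal baseline

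*SAP*

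**What the plan says.** SAP 10.3.3 plans a laboratory table showing "the number and percentage of subjects in each treatment group with normal baseline values who had at least one pre-specified markedly abnormal value". SAP 10.4.1.2 plans the vital-signs equivalent, "displaying the number and percentage of subjects with normal baselines who had one or more pre-specified markedly abnormal treatment-emergent values".

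For haematology and chemistry, SAP 10.3.2 compares baseline with the worst in-treatment value, in "tables presenting the changes from *Low* or *Normal* to *High* and from *High* or *Normal* to" Low. For urinalysis, SAP 10.3.5 summarises the "number of subjects with change from *Absent* at baseline to *Present* during trial". No shift table is planned for vital signs.

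The criteria are in SAP 15.5. Most rows of Table 6 are fixed thresholds, but alkaline phosphatase requires "> 3xULN and 25% increase from" baseline, and the dipstick rows require a rise of at least 2 units. Under Table 7, "To be identified as markedly abnormal, a treatment value must meet the criterion value and also the specified change" from baseline. The body-weight row has no criterion value (the entry is None), only a change of 7% or more in either direction.

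**The concern.** A marked worsening matters for safety whether the starting value was normal or slightly raised. These tables are the only pre-specified counts by arm that use objective thresholds, and both sets are conditioned so that same-direction worsening from an abnormal baseline drops out.

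Such women can enter the trial. Protocol 4.1 requires normal prolactin and TSH and caps FSH and LH, but neither 4.1 nor 4.2 sets a limit on safety chemistry, haematology or vital signs, and BMI may be as high as 38. The SAP itself provides for Low and High baselines in 10.3.2 and for listing abnormal baseline values in 10.3.4. Safety is a stated objective, and laboratory values are a stated safety endpoint (Protocol 2).

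**Working it through.** There is no figure in the plan to reproduce. The check is which subjects enter which table.

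**Step 1: enumerate the cells.** Cross three baseline categories (Low, Normal, High) with five worst in-treatment categories (Low, Normal, High, markedly Low, markedly High). This gives 3 × 5 = 15 cells, to which the rules of 10.3.2 and 10.3.3 are applied.

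| Baseline | Worst value | Cells | Shift table | Markedly-abnormal table |
|---|---|---|---|---|
| Normal | markedly High or markedly Low | 2 | counted | counted |
| Normal | High or Low, not marked | 2 | counted | not applicable |
| Low | High, marked or not | 2 | counted | not counted |
| High | Low, marked or not | 2 | counted | not counted |
| High | markedly High | 1 | **not counted** | **not counted** |
| Low | markedly Low | 1 | **not counted** | **not counted** |
| Any | Normal, or same category without a marked value | 5 | not counted | not applicable |

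Two cells hold a marked worsening that neither table counts. Moves from one abnormal side to the other are caught by the shift table. Urinalysis behaves in the same way: dipstick blood going from 1+ to 3+ meets the 2-unit criterion in Table 6, but it is Present to Present in the shift table, and 10.3.3 drops it if 1+ is not a normal baseline.

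**Step 2: a worked case.** Suppose an arm has 15 women, 14 with normal ALT who stay normal and one at 1.3×ULN who rises to 6×ULN. The criterion is >3×ULN.
- As planned: 0 of 14 women with normal baseline.
- Counting all women whose baseline did not already exceed 3×ULN: 1 of 15 = 6.7%.

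**Step 3: the alkaline phosphatase clause.** Let b be the baseline and v the later value. If b ≤ ULN and v > 3×ULN, the relative rise is v/b − 1 > 3 − 1 = 200%, so the 25% condition is always met. The clause can exclude someone only if v > 3×ULN while v < 1.25b, which needs b > 3/1.25 = 2.4×ULN. The normal-baseline condition removes every such woman, so the clause never operates.

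**Step 4: body weight.** The row is defined by change alone, and the SAP prints no reference range for vital signs. There is nothing against which a baseline weight can be called normal, so the filter cannot be applied to this row as written.

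**The case against.** The strongest reply is that nothing is hidden.

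- **Other outputs.** SAP 10.3.1 and 10.4.1.1 summarise all subjects with data, giving minimum and maximum for observed values and for change; Protocol 9.8.3 makes the laboratory change summary by treatment group. The woman in Step 2 would probably be the printed maximum of her arm. Protocol 8.1 makes a clinically significant laboratory or vital-sign finding an adverse event, SAP 10.2 treats worsening of a pre-existing condition as treatment-emergent, and those events are tabulated by arm. SAP 10.3.4 and 10.4.1.3 list every abnormal value by treatment group.
- **Purpose.** Restricting to normal baselines isolates new abnormalities. It is a disclosed conditional count.
- **Criteria.** A clause that is redundant in one row is not a general contradiction. Pulse falling from 60 to 50 is a drop of 10 and fails the 15-beat condition; 70 to 50 is a drop of 20 and meets it. The lower vital-sign rows and the dipstick rows thus do work from normal baselines.
- **Entry and use.** Exclusion criterion 2 removes clinically important organ disease. Safety analysis is descriptive (Protocol 9.8.1), and no decision rule uses these tables.

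Most of this stands. A reader might infer that the woman is in no by-arm safety table at all; the first item shows that the documents do not support that. A reader might also infer that the filter defeats the change conditions throughout Tables 6 and 7; only the alkaline phosphatase clause and the body-weight row are shown to be affected, and the SAP nowhere says that change conditions were intended for abnormal baselines.

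The reply does not restore the count. A mean or maximum does not say how many women worsened. The adverse event route depends on the investigator's judgement and on timing. Protocol 7.6.5.1 schedules post-baseline safety laboratories only at End-of-Study or early termination. In pregnant women End-of-Study is 2 to 4 weeks after the second positive test, at which treatment ends. A laboratory event is dated to the sample (Protocol 8.2.2), so it would fall outside the window of 2 days (Protocol 9.8.2) or 5 days (SAP 10.2). Exclusion criterion 2 does not remove mild abnormalities.

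**Conclusion.** The point holds as a gap in the threshold-based counts. Same-direction marked worsening from an abnormal baseline is left out of SAP 10.3.3, 10.4.1.2, 10.3.2 and 10.3.5. Such a subject is seen only in summary statistics, in listings and, conditionally, in the adverse event tables. One alkaline phosphatase clause is inoperative, and the body-weight row cannot be produced as written.

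One uncounted case is 1/15 = 6.7 percentage points of an arm, assuming the planned 60 women divide equally over four arms. The expected number of such cases cannot be given: it needs both the prevalence of abnormal baselines and the chance of marked worsening from them, and the documents state neither. A downward bias of known size is therefore not shown. The primary result is unaffected. This is an inexpensive improvement that should be made before the tables are programmed.

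**What to change.** In SAP 10.3.3 and 10.4.1.2, replace the normal-baseline condition with: subjects whose baseline value did not already meet the markedly abnormal criterion value. For rows defined only by change from baseline (body weight, dipstick), include all subjects with a baseline.

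Use those same at-risk subjects, with a baseline and at least one post-baseline value, as the denominator. A denominator of all subjects would include women who cannot enter the numerator. Keep the normal-baseline count as a sub-row, so that new abnormalities can be told apart from worsening of existing ones. The alkaline phosphatase clause then operates for baselines above 2.4×ULN and up to 3×ULN. State at the same time whether the End-of-Study sample falls within the treatment period to which 10.3.3 refers.

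The cost is two SAP sentences and one programming filter; no new data and no change in trial conduct are needed. The small downside is that a few women with a raised baseline who drift just over a fixed threshold, for example ALT from 2.9 to 3.1×ULN, will be counted; the sub-row makes them identifiable.

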6.2.4 Progesterone and Pregnancy Monitoring

Treatment Days 19, 21, 23, 25, and 27

- Blood collection for P₄
- Concomitant medication use
- Adverse event and unanticipated adverse device effect assessment
- 12-lead ECG (for subjects who report chest pain or are symptomatic of chest pain)
- LutrePulse Omnipod treatment continues for luteal phase support for subjects with confirmed LH surge

Interview and study drug return

Non-pregnant subjects will visit the site to return used and unused study drug product, their subject diary card and the OmniPod delivery system and report the day menstruation began and duration of menses, if applicable. Gonadotropins for one treatment cycle as well as compensation toward a future IVF cycle could be offered to all non-pregnant subjects who participated in and completed the study (had at least 14 days of study medication) and completed an End-of-Study visit. No study-related follow-up will be conducted regarding such cycles.

14 (+ 4) days after LH surge and 3 days thereafter

Two positive serum pregnancy tests are required to confirm biochemical pregnancy 14 (+ 4) days after LH surge and 3 days thereafter. If only one of the 2 tests is positive, the subject will return within 5 days (unscheduled visit) to confirm pregnancy with another serum pregnancy test. Subjects with 2 negative pregnancy tests will complete an End-of-Study Visit on the day of the second negative pregnancy test.

- Serum pregnancy test
- Concomitant medication use
- Adverse event and unanticipated adverse device effect assessment
- 12-lead ECG (for subjects who report chest pain or are symptomatic of chest pain)

2 to 4 weeks after second positive serum pregnancy test

- TVUS to detect gestational sac and fetal heartbeat
- If fetal heartbeat is not documented, the subject may return within 7 days for another TVUS
- Concomitant medication use
- Adverse event and unanticipated adverse device effect assessment
- 12-lead ECG (for subjects who report chest pain or are symptomatic of chest pain)

End-of-Study Visit

The End-of-Study Visit is performed in conjunction with the final TVUS visit 2 to 4 weeks after the second positive serum pregnancy test or on the day of the second negative serum pregnancy test for subjects who do not become pregnant (2 negative serum pregnancy tests).

- Gynecological examination, including breast exam
- Physical examination, including weight
- Vital signs (blood pressure, heart rate, and oral temperature)

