7.6.5 Clinical Laboratory Tests

7.6.5.1 Hematology, Serum Chemistry, and Urinalysis

A standard panel, as well as the following safety laboratory tests, will be performed at Screening and at the End-of-Study Visit (or at the time of early termination). A 10 hour overnight fast is required prior to collecting the blood samples. The total amount of blood required for safety assessments is approximately 80 mL.

Hematology: red blood cell count, white blood cell count, hematocrit, hemoglobin, platelet count, and differential count.

Serum Chemistry: fasting glucose, blood urea nitrogen, creatinine, potassium, sodium, chloride, calcium, total protein, albumin, total bilirubin, alkaline phosphatase, aspartate aminotransferase, alanine aminotransferase, and gamma glutamyl transferase.

Urinalysis: leukocyte esterase, blood, pH, specific gravity, protein, glucose, urobilinogen, and microscopic if positive for blood or protein.

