10.2 Adverse Events

An AE is any untoward medical occurrence in a patient or clinical investigation subject administered a pharmaceutical product and which does not necessarily have to have a causal relationship with this treatment.

All Adverse Events (AEs) and unanticipated adverse device effects will be listed, documenting all information as on the eCRF. Verbatim terms of AEs will be coded to the MedDRA preferred terms (PT) and related system organ classes (SOC) using the Medical Dictionary for Regulatory Activities (MedDRA). The latest MedDRA version available at the time of interim analysis or final analysis will be applied.

A treatment emergent adverse event (TEAE) will be any adverse event occurring after start of IMP and within 5 days after the last application, or a pre-treatment adverse event or pre-existing medical condition that worsens in intensity after start of IMP and within 5 days after the last application. All adverse events occurring after 5 days from the last application will be categorized as post-treatment adverse events.

Note: Collection of AEs on the eCRF will begin after the informed consent form (ICF) is obtained from the patient. Any AE prior to the signed ICF will be recorded in the medical history.

Written narratives will be issued for all serious AEs (including deaths) and AEs leading to withdrawal.

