10.2.1 Partial/Missing Dates for Adverse Events

For any adverse event that has a missing or incomplete start date, a query will be issued to capture the full date. If only a partial date is reported for the start of an AE, a complete date will be estimated using the following algorithm:

- Only the year is reported (i.e., missing the month and day): The date of the first dose of investigation product will be used as the start of the AE.
- The year and month are reported (i.e., missing the day): The first day of the month will be imputed or the date of the first dose, whichever is later.

The month and day are reported (i.e., missing the year): Only situations where the year is self-evident will be allowed.

Date: 07 Dec 2017 E-Statistical Analysis Plan-21977; Ver. 1.0 Supersedes: None

Page 26 of 59

No imputation will be applied to the incomplete AE end date. The rationale is that one should have a start date for all subject AEs but may not have end dates for AEs that resolve after subject is off study or AEs that are continuing.

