10.5.3 Ovarian Hyperstimulation Syndrome (OHSS)

The frequency and severity of ovarian hyperstimulation syndrome will be presented in by-patient listings and summary tables as for AEs.

Date: 07 Dec 2017 E-Statistical Analysis Plan-21977; Ver. 1.0 Supersedes: None Page 30 of 59

11 Interim analyses

Two interim analyses are planned after approximately 9 and 12 patients per arm complete the study. The details of the interim analysis strategy are described in Section 9.2.

An independent data monitoring committee consisting of two unblinded clinicians and one unblinded statistician will be set up to review the interim analysis study results and make recommendations for the direction of the study, in accordance with the adaptive design decision-making rules specified in Section 9.2.1. In addition, independent statistician and programmer will be identified to generate the data analysis output. Individuals involved in the first and second interim analysis of the study will not be involved in the conduct of the study afterwards; individual patient identification will not be released to anyone who is directly involved in the conduct of the study.

The interim analysis process, the measures used to protect the blind and the integrity of the study, the communication plan, and the confidentiality agreement will be described in a separate document.

Date: 07 Dec 2017 E-Statistical Analysis Plan-21977; Ver. 1.0 Supersedes: None Page 31 of 59

12 Deviations from protocol analysis

13 References

- [1] International Federation of Pharmaceutical Manufacturers and Associations. Medical Dictionary for Regulatory Activities (MedDRA). Version 10.1. Reston, Virginia, USA; 2008.
- [2] WHO Collaborating Center for International Drug Monitoring. WHO Drug Dictionary. July 2008 edition. Uppsala, Sweden; 2008.
- [3] SAS Institute Inc. SAS Version 9.1. Cary, NC, USA; 2002-2003.
- [5] Jung, S.H. Stratified Fisher's exact test and its sample size calculation. Biometrical J. 2014;56. doi: 10.1002/bimj.201300048.
- [6] van Elteren, P. H. (1960). "On the combination of independent two-sample tests of Wilcoxon," Bulletin of the International Statistical Institute, 37, 351-361.

14 Tables, Listings and Figures

The document with tables, figures and listings (TLF) shells will be presented in a separate document.

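### As written, three SAP safety tables omit pregnant women's only scheduled post-baseline value, late non-serious OHSS has no assured by-arm table, and unresolved partial dates turn known pre-dose events into treatment-emergent ones

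*SAP*

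**What the plan says.** **Which values the tables use.** SAP 10.3.3 reports subjects with normal baselines who "had at least one pre-specified markedly abnormal value anytime during the treatment period". In SAP 10.3.2, "shift tables will be prepared to compare baseline values to the worst in-treatment value". SAP 10.4.1.2 limits the markedly abnormal vital-sign table to treatment-emergent values. SAP 10.3 sets the outer limit for labs: "Treatment-emergent laboratory data will include tests completed after the first dose of IMP through the residual time of drug effect". SAP 10.4.1 has a matching sentence for vital signs. Neither gives a number of days.

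**When the values are taken.** Protocol 7.6.3 and 7.6.5.1 schedule vital signs and safety labs at Screening and End-of-Study only (for labs, also at early termination). Protocol 3.1 ends treatment once two serum pregnancy tests agree. For pregnant women, "The End-of-Study Visit is performed in conjunction with the final TVUS visit 2 to 4 weeks after the second positive serum pregnancy test" (Protocol 6.2.4), and Protocol 3.1 allows a repeat scan within 7 more days. Women with two negative tests have the visit on the day of the second test (Protocol 4.4).

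**Adverse events and OHSS.** SAP 10.2: "All adverse events occurring after 5 days from the last application will be categorized as post-treatment adverse events". Protocol 9.8.2 uses 2 days after the last dose. SAP 10.5.3: "The frequency and severity of ovarian hyperstimulation syndrome will be presented in by-patient listings and summary tables as for AEs". The incidence tables in SAP 10.2.3 by system organ class and preferred term are for treatment-emergent events.

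**Partial dates.** When the day of an AE start is missing and a query has not recovered it, SAP 10.2.1 applies this rule: "The first day of the month will be imputed or the date of the first dose, whichever is later".

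**The concern.** Shift and markedly abnormal tables exist to show how many women crossed a threshold in each arm. If a woman's only scheduled post-baseline sample lies outside the window because she conceived, she cannot contribute an abnormal value. Conception is expected almost only on active drug, so the omission would make the active arms look cleaner than the collected data. The percentage in SAP 10.3.3 can also be read as taking every subject with a normal baseline as its denominator, in which case these women would count as free of abnormality without having been assessed.

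OHSS frequency and severity is a named safety endpoint with no time limit (Protocol 2, SAP 2.4.7), so a tabulation that stops shortly after treatment does not fully deliver it. The date rule works the other way: it adds events that cannot have been caused by the drug.

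**Working it through.** **Window check.** The protocol allows 2 days after the last dose and a pod is worn for 3 days: 3 + 2 = 5 days after the last application. This reproduces the SAP figure for a fully worn last pod. If the last pod is stopped w days after application, the SAP window runs 5 − w days past the last dose: 5, 4, 3 or 2 days for w = 0 to 3.

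**(a) Pregnant women.** Take treatment as stopping on the day of the second positive test.
- End-of-Study falls 14 to 28 days later, or up to 28 + 7 = 35 with a repeat scan.
- Adding 0 to 3 days since the last pod was applied gives 14 + 0 = 14 to 35 + 3 = 38 days after last application.
- Of the 22 × 4 = 88 combinations of visit day and pod day, none is within 5 days.
- If treatment ran on while results were awaited, the delay would have to reach 14 − 5 = 9 days before the earliest visit came inside.

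**Non-pregnant women.** A visit on the day of the second negative test is 0 to 3 days after last application, so always inside. A woman who stops early is seen within 3 days (Protocol 4.4): at most 3 days after last dose, or 3 + 3 = 6 after last application. That is at most one day outside either window. The large gap is therefore tied to pregnancy.

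**Number affected.** Inputs: about 15 per arm (SAP Table 1); ovulation 60%, 65%, 70% and placebo 1% (SAP 3.2); conception per ovulatory woman c, which the documents do not give, assumed 10 to 50%.
- Active ovulators: 15 × (0.60 + 0.65 + 0.70) = 29.25.
- c = 0.10: 29.25 × 0.10 = 2.9 women. c = 0.50: 29.25 × 0.50 = 14.6 women, of 45.
- Placebo at c = 0.50: 15 × 0.01 × 0.50 = 0.075 of 15.
- With early stopping, SAP 15.2.3 Scenario 1 averages 13.1 per active arm: 13.1 × 1.95 = 25.5 ovulators, hence 2.6 to 12.8 women.

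**Urinalysis.** SAP 10.3.2 counts absent-to-present changes within treatment; SAP 10.3.5 counts the same change over the whole trial. The two tables would differ for exactly these women.

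**(b) OHSS.** The confirmatory tests fall 14 (+4) days after the LH surge and 3 days later, so treatment runs to about 14 + 3 = 17 to 18 + 3 = 21 days after surge. OHSS up to then, and in the short tail, is treatment-emergent. Measured from the protocol's 2-day limit, a further 14 − 2 = 12 to 28 − 2 = 26 days of AE collection precede a pregnant woman's End-of-Study visit. An onset in that stretch is post-treatment, and the SAP names no post-treatment AE table.

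**(c) Partial dates.** Imputed start = max(first of reported month, first-dose date). An event recorded as February with first dose on 15 March gives max(1 Feb, 15 Mar) = 15 March and becomes treatment-emergent. AEs are collected from consent (SAP 10.2), and screening runs up to 60 days and includes 10 days of medroxyprogesterone. Applying the rule to every onset from Day −60 to Day −1 for every first-dose date in a 366-day year (366 × 60 = 21,960 cases) moves all 21,960 to first dose. Some have onset in the same month as first dose, where the order is unknown and the convention is reasonable. The fault is in the cases whose reported month already precedes dosing. The year-only rule has the same fault when the reported year does.

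**The case against.** A reader might infer that pregnant women's labs disappear from the safety tables altogether. They do not. SAP 10.3 defines the end-of-trial value as the last post-baseline observation, with no treatment limit, and it feeds the mean-change tables (10.3.1). The values also stay in the urinalysis table (10.3.5) and the abnormal-value listings (10.3.4), and vital signs are handled likewise. Everything Protocol 9.8.3 promises is kept. Exclusion from the other tables depends on a residual drug-effect period that is never given a length, and the table shells are a separate document. This narrows the point but does not remove it: means and listings do not count threshold crossings by arm, and no window stated in the documents would bring these values in.

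It is also tempting to say that any OHSS in follow-up is lost. Onset within 5 days of last application remains treatment-emergent. Severe OHSS needing medical or surgical intervention is an SAE (Protocol 7.6.6) and may reach the SAE table. The SAP's tables of all AEs and of SAEs are not expressly limited to treatment-emergent events, and every case is listed by patient. The documents give no OHSS rate or onset timing, so an undercount cannot be sized. Nor do they establish that OHSS will be graded on the 3-point AE intensity scale. That is only an inference from SAP 10.5.3, which does not cite Protocol Table 2.

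On dates, a query comes first, the number of unresolved cases may be zero, and counting doubtful events against treatment is a conservative convention. That defence covers events of unknown order, not those whose month is known to precede dosing.

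Finally, values taken two or more weeks after treatment, in early pregnancy, are in time post-treatment. Mixing them unmarked into on-treatment tables would add pregnancy effects to the active arms. This stands, and the fix has to show them separately.

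**Conclusion.** The point holds in limited form. Read as written, the lab shift tables, the markedly abnormal lab table and the markedly abnormal vital-sign table omit the only scheduled post-baseline value of each woman followed to the pregnancy scan. That is about 3 to 15 of 45 active women against fewer than 0.1 of 15 on placebo. The range rests on the plan's ovulation rates, full enrolment and an assumed 10 to 50% conception per ovulatory woman; it is lower if the trial stops early.

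Non-serious OHSS with onset more than 5 days after the last application has no assured by-arm summary, though the endpoint has no time limit. When the query fails, the date rule makes events from a month known to precede dosing treatment-emergent; how many is unknown.

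The 2-day and 5-day limits might be read as a conflict between protocol and SAP, but they agree for a fully worn last pod. Safety analysis is descriptive (Protocol 9.8.1), so the efficacy conclusion is untouched. The SAP should still be corrected, because the gap in (a) falls on one side of the comparison.

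**What to change.** - **SAP 10.3.2, 10.3.3, 10.4.1.2:** use all post-baseline values through End-of-Study, with those after the TEAE window flagged or shown separately. Take subjects with a post-baseline value as the denominator. Align urinalysis in 10.3.2 with 10.3.5.
- **SAP 10.5.3:** tabulate OHSS by arm and Protocol Table 2 grade from first dose to End-of-Study, split into on-treatment and post-treatment onset.
- **SAP 10.2.1:** impute the first-dose date only when the known month and year could be on or after first dose and the event did not end before it. Otherwise classify the event as pre-treatment.

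The cost is SAP wording, matching table shells and a few extra outputs. No new data are needed and no trial procedure changes. The small downside is that some late values will reflect early pregnancy, which the flag or split makes visible.
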